		
P-gp inhibitors), administer an Edoxaban dose of 15 mg once-daily together with an appropriate VKA dose. Edoxaban 15 mg once-daily is not indicated as monotherapy, as it may result in decreased efficacy. It is only indicated in the process of switching from Edoxaban 30 mg once-daily to VKA, together with an appropriate VKA dose.
 
Subjects should not take a loading dose of VKA in order to promptly achieve a stable INR of 2.0 to 3.0 (numbers inclusive) [Japan: 1.6-2.6 in subjects aged ≥ 70 (numbers inclusive)]. It is recommended to take into account the maintenance dose of VKA if the subject was previously taking a VKA or to use valid INR driven VKA treatment algorithm, in accordance with local practice.
 
Once an INR ≥ 2.0 is achieved [Japan: ≥ 1.6 in subjects aged ≥ 70], Edoxaban should be discontinued. Most subjects (85%) should be able to achieve an INR ≥ 2.0 [Japan: 1.6 in subjects aged ≥ 70 (numbers inclusive)] within 14 days of concomitant administration of Edoxaban and VKA. After 14 days it is recommended that Edoxaban is discontinued and the VKA continued to be titrated to achieve an INR of 2.0-3.0 (numbers inclusive) [Japan: 1.6-2.6 in subjects aged ≥ 70 (numbers inclusive)]. It is recommended that during the first 14 days of concomitant therapy the INR is measured at least three times just prior to taking the daily dose of Edoxaban to minimize the influence of Edoxaban on INR measurements. Concomitant Edoxaban and VKA can increase the INR post Edoxaban dose by up to 46%.
 
Parenteral option: Discontinue Edoxaban and administer a parenteral anticoagulant and VKA at the time of the next scheduled Edoxaban dose. Once a stable INR of ≥ 2.0 is achieved [Japan: ≥ 1.6 in subjects aged ≥ 70], the parenteral anticoagulant should be discontinued and the VKA continued.

Edoxaban	Other non-VKA OAC drugs	Discontinue Edoxaban and start the non-VKA anticoagulant at the time of the next scheduled dose of Edoxaban.
Edoxaban	Parenteral anticoagulants	These agents should not be administered simultaneously. Discontinue Edoxaban and start the parenteral anticoagulant at the time of the next scheduled dose of Edoxaban.

CrCL = creatinine clearance; INR = international normalized ratio; OAC = Oral anticoagulant(s);
P-gp = P-glycoprotein; VKA = vitamin K antagonist

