6.6. Post-treatment Follow-up Visit

The Follow-up Visit will be 30 days (\pm 7 days) after the last study treatment.

The Follow-up Visit activities are listed below:

- Perform physical examination;
- Record vital signs (blood pressure and heart rate after the subject has been resting at least 5 minutes in a sitting position; body temperature, and weight);
- Check INR and recommend any dose adjustments to subject's personal physician;
- Blood draw for analysis by an accredited/certified local laboratory, the clinical laboratory tests (see Section 9.9) or if results are available from standard of care and are within 15 days prior to the visit these values may be used instead of requiring an additional blood draw;
- Assessment and recording of (S)AEs and suspected clinical events since last visit; Assessment of any hospitalization for cardiovascular causes (such as shock, arrhythmia, cardiac rupture, stroke, aneurysms, stent occlusions, etc.) or bleeding;
- Record any changes in concomitant medications;
- Confirm consent to participate in Post Discontinuation/Follow-up Contact;
- For childbearing potential female subjects, a urine pregnancy test (e.g., dipstick test) will be performed.

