9.1. Adverse Event Collection and Reporting

All clinical AEs (see Section 9.3.1 for definitions) occurring after the subject signs the Informed Consent Form and up to 30 days after the last dose of study medication (i.e., the follow-up period), whether observed by the Investigator or reported by the subject, will be recorded on the Adverse Event eCRF page.

Subjects who permanently discontinue study medication but continue in the study will be followed up every 6 months for collection of vital status (not vital signs) including collection of SAE and/or endpoint event reporting until the end of study (see Section 6.7).

Medical conditions (including laboratory values/vital signs that are out of range) that were diagnosed or known to exist prior to Informed Consent will be recorded as part of medical history.

All serious adverse events (SAEs), are to be reported according to the procedures in Section 9.6.

- All laboratory results, vital signs, ECG, and any other imaging results or findings should be appraised by the Investigator to determine their clinical significance. Isolated abnormal laboratory results, vital sign findings, or ECG findings (i.e., not part of a reported diagnosis) should be reported as AEs if they are symptomatic, lead to study drug discontinuation, dose reduction, require corrective treatment, or constitute an AE in the Investigator's clinical judgment.
- At each visit, the Investigator or qualified designee will determine whether any AEs have occurred by evaluating the subject. Adverse events may be directly observed, reported spontaneously by the subject, or by questioning the subject at each study visit. Subjects should be questioned in a general way, without asking about the occurrence of any specific symptoms. The Investigator must assess all AEs to determine seriousness, severity, and causality, in accordance with the definitions in Section 9.3. The Investigator's assessment must be clearly documented in the site's source documentation with the Investigator's signature.

Always report the diagnosis as the AE or SAE term. When a diagnosis is unavailable, report the primary sign or symptom as the AE or SAE term with additional details included in the narrative until the diagnosis becomes available. If the signs and symptoms are distinct and do not suggest a common diagnosis, report them as individual entries of AE or SAE.

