9.5. Reporting SAEs/AEs

9.5.1. Documentation

To effectively evaluate the safety profile of the study treatments, this study will report all (S)AEs occurring after the subject signs the IC and as long as the subject remains in the study or until the study is terminated by the Sponsor (i.e., the end of the study), whether observed by the Investigator or reported by the subject. All AEs will be recorded on the AE/Outcome eCRF page(s) and include:

- Any components of the study endpoint assessments (see Section 7);
- AEs that meet seriousness criteria (see Section 9.3.4);
- AEs that result in interruption or discontinuation of the assigned study treatment;
- Any other AE.

All laboratory results and vital signs should be evaluated by the Investigator regarding clinical significance. Isolated abnormal laboratory results or vital sign findings that are not part of a diagnosis should be reported as AEs or SAEs. Medical conditions (including laboratory values/vital signs that are out of range) that were diagnosed or known to exist prior to IC will be recorded as part of medical history.

All SAEs are to be reported as long as the subject remains in the study or until the study is terminated by the Sponsor (i.e., the end of the study) and according to the procedures in Section 9.6. Always report the diagnosis as the AE or SAE term. When a diagnosis is unavailable, report the primary sign or symptom as the AE or SAE term with additional details included in the narrative until the diagnosis becomes available. If the signs and symptoms are distinct and do not suggest a common diagnosis, report them as individual entries of AE or SAE. For events that are serious due to hospitalization, the reason for hospitalization must be reported as the SAE (diagnosis or symptom requiring hospitalization).

AEs may be directly observed, reported spontaneously by the subject or by questioning the subject at each study visit. Subjects should be questioned in a general way, without asking about the occurrence of any specific symptoms. The Investigator must assess all AEs to determine seriousness, severity, and causality, in accordance with the definitions in Section 9.3.5 and Section 9.3.6. The Investigator's assessment must be clearly documented in the site's source documentation with the Investigator's signature.

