9.9. Clinical Laboratory Evaluations

Information will be entered in the case report form on whether or not measured, date of measurement, and measurement results and the local laboratory ranges for the following items.

The results will be reviewed and compared to the local accredited/certified laboratory's normal ranges. The visits at which these samples will be collected are shown in the schedule of assessments (Table 17.1).

The following safety laboratory evaluations are performed:

- **Serum Chemistry Panel**
 - Creatinine
 - Sodium (Na⁺)
 - Potassium (K⁺)
 - Chlorine (Cl⁻)
 - Blood urea nitrogen (BUN)
 - Glucose
- **Complete Blood Count (CBC) Panel:** Including Hemoglobin, Hematocrit, WBC, Platelet Count
- **INR** (only for subjects on VKA)
- **Urine pregnancy test** (e.g., dipstick test), for childbearing potential female subjects at Randomization, 3 months, 12 months, 24 months, and End of Treatment Visits.
- **Serum pregnancy test** at time of Screening for women of child bearing potential who are female subjects who are of child bearing potential.

A liver function panel (total bilirubin [conjugated/unconjugated performed when total serum bilirubin \geq 2 mg/dL], ALT, AST, ALP) will be performed at Screening (only if a recent, within the 15 days before randomization, is not available), and at the 6 Month and 12 Month Visits.

All other assessments are collected from local laboratory results for tests done as part of routine care. Local laboratory assessments are used for parameters required to verify eligibility and for parameters that require monitoring according to local routine.

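### Protocol Sections 9.5.1 and 9.1 give different rules for when an isolated abnormal laboratory value is an adverse event, and through routine INR testing the difference falls mainly on the VKA arm

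*Combined protocol and SAP*

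**What the plan says.** Three places in the protocol decide whether an isolated abnormal laboratory or vital sign finding becomes an AE.

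- **Section 9.5.1 (Documentation):** "Isolated abnormal laboratory results or vital sign findings that are not part of a diagnosis should be reported as AEs or SAEs". The sentence before it reads "All laboratory results and vital signs should be evaluated by the Investigator regarding clinical significance", but the outcome of that evaluation is not made a condition for reporting.
- **Section 9.1 (Adverse Event Collection and Reporting):** such findings "should be reported as AEs if they are symptomatic, lead to study drug discontinuation, dose reduction, require corrective treatment". A last ground is that the Investigator judges the finding to be an AE.
- **Section 9.3.1 (Definition of Adverse Event):** Investigators are responsible for deciding which abnormal laboratory findings count as AEs.

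Section 9.9 lists INR among the safety laboratory evaluations, "only for subjects on VKA". For laboratory results in general it says "The results will be reviewed and compared to the local accredited/certified laboratory", meaning that laboratory's normal ranges. Sections 5.2.1.2 and 6.4 prefer monthly INR in VKA subjects. Section 6.4 requires an INR at a study visit only if the last one is more than 3 months old or the target has been hard to reach.

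Section 11.5.1 summarises TEAEs by treatment group, by relationship and by severity, with a further table of TEAEs reported by at least 5% of subjects in either group. A subject is counted once per preferred term.

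**The concern.** Two sections give different answers for the same finding, and nothing says which prevails. One cannot simply assume that 9.5.1 defers to 9.1, because the two also differ on how long AEs are collected: to 30 days after the last dose in 9.1, and for as long as the subject is in the study in 9.5.1. A site working from 9.5.1 would enter findings that a site working from 9.1 would not.

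For most laboratory tests this is noise shared by the arms. INR is different. It is measured repeatedly on treatment in VKA subjects and has no routine counterpart on edoxaban, so extra entries would fall mainly on the VKA side and make edoxaban look better in the TEAE tables. The trial is open-label, and blinded adjudication protects the clinical endpoints but not these counts. Section 9.3.6 classes an event as related if, among other things, known pharmacology predicts it, so a high INR on VKA could also enter the related-TEAE counts.

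**Working it through.** **1. The texts side by side.**

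| Isolated finding | 9.5.1 read literally | 9.1 |
|---|---|---|
| No symptoms, no action, not judged an AE | AE | not an AE |
| Leads to a dose reduction | AE | AE |
| Symptomatic, or needs corrective treatment | AE | AE |

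The rules part in the first row. The second row matters for INR. The protocol's definitions make VKA a study medication, and hence a study drug, so an INR that prompts an ordinary VKA dose reduction already meets the 9.1 wording. Section 9.5.1 therefore enlarges an imbalance that 9.1 already contains.

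**2. What counts as abnormal.** Section 9.9 compares results with local normal ranges and not with the therapeutic target. The documents do not give those ranges. If a laboratory uses a range for untreated people, even an INR within 2.0 to 3.0 could be flagged.

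**3. Where INR is measured.** Routine on-treatment INR is confined to VKA subjects. For edoxaban subjects moving to VKA, Section 5.2.1.1.2 recommends that "during the first 14 days of concomitant therapy the INR is measured at least three times". Section 6.6 lists "Check INR and recommend any dose adjustments" at the follow-up visit without naming an arm. That visit is 30 days (±7) after the last study treatment, and the TEAE window closes 30 days after the last dose, so these INRs fall at least partly inside it.

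**4. Size, as illustration only.** The documents state no figure to reproduce. Let q be the assumed share of INRs called abnormal and m the number of INRs per VKA subject, with INRs treated as independent.

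- Expected entries per subject = m × q
- P(at least one) = 1 − (1 − q)^m

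Year 1:

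| q | Monthly, m = 12 | Four a year, m = 4 |
|---|---|---|
| 0.35 | 12 × 0.35 = 4.2 entries; 1 − 0.65^12 = 99.4% | 1.4 entries; 1 − 0.65^4 = 82% |
| 0.25 | 3.0 entries; 1 − 0.75^12 = 96.8% | 1.0 entry; 1 − 0.75^4 = 68% |

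Over 24 months (the anticipated median follow-up), with 1400 / 2 = 700 VKA subjects:

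| q | Monthly, m = 24 | About quarterly, m = 8 |
|---|---|---|
| 0.05 | 840 entries; 71% | 280 entries; 34% |
| 0.20 | 3360 entries; 99.5% | 1120 entries; 83% |
| 0.50 | 8400 entries; >99.9% | 2800 entries; 99.6% |

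Correlation between INRs in the same subject would lower every percentage. The once-per-term rule means that the incidence tables reflect the percentages and not the entry counts.

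**5. The same literal rule in both arms.** Section 9.9 lists six chemistry and four blood count tests for all subjects, and the schedule has three post-baseline visits in year 1 (months 3, 6 and 12). If 5% of results are abnormal, independently, 1 − 0.95^(10 × 3) = 78.5% of subjects in each arm have at least one. Adding INR in the VKA arm gives:

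- q = 0.25, m = 4: 1 − 0.2146 × 0.3164 = 93.2%, an excess of 14.7 percentage points
- q = 0.35, m = 12: 1 − 0.2146 × 0.0057 = 99.9%, an excess of about 21 percentage points

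On these assumptions the any-TEAE excess is about 15 to 21 points, not the 68 to 99% that INR alone suggests. Ordinary clinical AEs in both arms would shrink it further. INR-specific preferred terms would keep most of the imbalance.

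**The case against.** The best defence is that 9.5.1 is only loosely drafted. Section 9.3.1 gives the decision to the Investigator, 9.1 includes the Investigator's judgment, and the request in 9.5.1 to evaluate clinical significance would have little purpose if every isolated value were automatically an AE. Read together, the sections may mean what 9.1 says. That is a fair account of the likely intent, but the sentence in 9.5.1 still has no condition, and a site can follow it as written.

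Three further objections stand and limit the point. First, INR is not unique to the VKA arm over the whole AE window, because edoxaban subjects can have INRs at transition and at follow-up. Second, the literal rule would raise AE counts in both arms through the other tests. Third, 9.1 itself captures INRs that lead to a VKA dose reduction, so a cross-reference alone would not remove the one-sidedness.

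A reader might infer that nearly every VKA subject would be counted on INR alone, through events that edoxaban subjects cannot have. The documents do not support this. The 99% figure needs an assumed in-range share of 0.65, independent INRs and monthly testing, which is preferred and not required. At four tests a year the same formula gives 68 to 82%.

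**Conclusion.** The inconsistency between 9.5.1 and 9.1 is real and should be reconciled. Its likely direction is extra INR-related TEAEs in the VKA arm, plus variation between sites. This rests on some sites applying 9.5.1 literally and on routine on-treatment INR being confined to VKA subjects.

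The size cannot be derived from the documents. Over 24 months the illustration runs from about a third of VKA subjects with an isolated INR entry (q = 0.05, quarterly testing) to nearly all of them, and it depends wholly on assumed inputs.

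The consequence is limited to TEAE tables in the safety analysis set, for which Section 11.5.1 plans summaries and no test. A reader might infer that the trial's main comparison is biased. It is not affected by this rule: NACE components are adjudicated blind by the Clinical Events Committee (Section 7.4.3), as is bleeding that needs medical attention (Section 9.1.1). This is a minor wording point that is worth making because it costs so little to correct.

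**What to change.** 1. Replace the 9.5.1 sentence with a reference to the criteria in 9.1, worded consistently with the Investigator's responsibility in 9.3.1.
2. Add one recording convention for both arms, applying to transition and follow-up INRs as well: an out-of-range INR without symptoms or bleeding that is handled by routine VKA titration is recorded as INR data and is not in itself an AE. This second step is needed because 9.1 alone would still count titration-related dose reductions.

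This is a reporting rule only and changes no dose or INR target. Little information is lost: INR values in VKA subjects already go into the eCRF, and Section 11.3 already plans a time-in-therapeutic-range summary for the VKA arm. The cost is a small amendment to 9.1 and 9.5.1 and fewer isolated INR entries in the AE listing. Sites would have less to report.

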9.6. Serious Adverse Event Reporting—Procedure for Investigators

- SAEs (see Section 9.3.4 for definition)
- Serious events that are also efficacy endpoints (stroke, transient ischemic attack, SEE, and myocardial infarction) and/or safety endpoints (bleeding) will be exempted from SAE processing and expedited reporting but will be captured in

the eCRF. These events are exempted as they are clinically anticipated events in the target treatment population and will be periodically reviewed by the DSMB in an unblinded manner to ensure prompt identification of any clinically concerning safety issues.

- **All SAEs resulting in death regardless of whether they are waived endpoints for processing and expedited reporting will be processed by the CRO for entry into the Sponsor's global safety database.**

In case of an occurrence of an SAE, the Investigator applies the following rules:

- Ensure appropriate medical treatment and decide whether to discontinue or interrupt any of the study medications or co-administered medications.
- Complete the initial AE/Outcome eCRF page upon event awareness.
- Record the event, its management, and outcome in the eCRF page.
- For SAEs, report in the eCRF **within 24 hours** of receiving knowledge of the occurrence. In the event that all the required information is not available, the information which is available is to be sent without delay (within 24 hours), and the outstanding data relayed as soon as available thereafter. Answer any queries related to the reported SAE as soon as possible.
- For AEs of special interest, report **within 24 hours** of receiving knowledge of the occurrence as defined for SAEs above.
- For AEs, obtain all data required incl. any information which, is only available after considerable delay (i.e., hospital reports, outcomes, resolution end dates), **as soon as available**.
- Components of the study endpoint assessments which result in death must be reported as SAEs **within 24 hours** of the Investigator's awareness.

9.7. Notifying Regulatory Authorities, Investigators, and Institutional Review Board/Ethics Committee

Daiichi Sankyo and/or CRO will inform Investigators, Institutional Review Boards (IRBs)/Ethics Committees (EtCs), and regulatory authorities of any suspected unexpected serious adverse reactions (SUSARs) occurring in other study centers or other studies of the investigational drug, as appropriate per local reporting requirements. Daiichi Sankyo and/or CRO will comply with any additional local safety reporting requirements. Detailed SAE processing, distribution and reporting will be laid out in sponsors SAE Flow Plan.

In the US, upon receipt of the Sponsor's notification of SUSARs that occurred with the study drug, unless delegated to the Sponsor, it is the Investigator's responsibility to inform the IRB/EtC per Sponsor's instruction.

In the European Economic Area (EEA) states, it is the Sponsor's responsibility to report SUSARs to all ECs.

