7.2. Primary Efficacy Parameters

NACE, i.e., the composite of all-cause death, MI, ischemic stroke, SEE, valve thrombosis, and major bleeding (ISTH definition)

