7.4. Secondary Endpoints (All Exploratory)

7.4.1. Secondary Efficacy Endpoints

- NACE defined as the composite of all-cause death, MI, ischemic stroke, SEE, valve thrombosis, and major bleeding (TIMI definition);
- NACE defined as the composite of all-cause death, MI, ischemic stroke, SEE, valve thrombosis, and major bleeding (BARC 3 or 5 definition);
- NACE defined as the composite of all-cause death, MI, ischemic stroke, SEE, valve thrombosis, and major and moderate bleeding (GUSTO definition);
- Major Adverse Cardiac Events (MACE), defined as the composite of all-cause death (excluding adjudicated non-cardiac death), MI, or repeat coronary revascularization of the target lesion;
- Major Adverse Cardiac and Cerebrovascular Events (MACCE), defined as the composite of all-cause death (excluding adjudicated non-cardiac death), MI, stroke (ischemic, hemorrhagic, or undetermined), or repeat coronary revascularization of the target lesion;
- Cardiovascular mortality
- Stroke (ischemic, hemorrhagic, or undetermined);
- Stroke (ischemic);
- Stroke (hemorrhagic);
- Stroke (undetermined)
- Fatal stroke (ischemic, hemorrhagic, or undetermined);
- Non-fatal stroke (ischemic, hemorrhagic, or undetermined);
- SEE;
- Myocardial Infarction;
- Valve thrombosis;

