7.4.3. Other Endpoints

- Number of hospital admissions, defined as ≥ 24 h stay in the hospital, due to cardiovascular causes (post TAVI and non-TAVI procedure related), including but not limited to overall, for bleeding, SEE, venous thrombosis, shock, arrhythmia, cardiac rupture, stroke, aneurysms, stent occlusions, etc.
 - Note: Hospital admissions due to cardiovascular causes include, but are not limited to the Emergency Department, ICU, and cardiovascular ward.
- Treatment satisfaction as assessed by the PACT-Q
- Health related quality of life as assessed by the EQ-5D-5L Questionnaire
- Optional: Sub-studies not interfering with the main study may be added including such as the assessment of biomarkers of hemostasis/coagulation and of cardiovascular risk such as but not limited to WBCT, TEG, and MEA, Hs-TnT, GDF-15, and cystatin-C.

All clinical endpoints will be analyzed as time to first occurrence of any of its components.

All relevant NACE components will be adjudicated by the CEC in a blinded manner. For all clinical endpoints blindly adjudicated by the CEC, the CEC's interpretation prevails and will be used in the statistical analysis.

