17.3. Cerebrovascular event

Stroke is defined as an abrupt onset, over minutes to hours, of a focal neurological deficit that is generally in the distribution of a single brain artery (including the retinal artery) and that is not due to an identifiable non-vascular cause (i.e., brain tumor or trauma). The deficit must either be associated with symptoms lasting more than 24 hours or result in death within 24 hours of symptom onset.

TIA is defined as an abrupt onset, over minutes to hours, of a focal non-fatal, neurological deficit in the distribution of a single brain artery (including the retinal artery) that lasts less than 24 hours and that does not satisfy the definition of stroke above.

17.3.1. Stroke is classified according to the VARC-2 definitions.

Diagnostic criteria

- Acute episode of a focal or global neurological deficit with at least one of the following: change in the level of consciousness, hemiplegia, hemiparesis, numbness, or sensory loss affecting one side of the body, dysphasia or aphasia, hemianopia, amaurosis fugax, or other neurological signs or symptoms consistent with stroke

- Stroke – duration of a focal or global neurological deficit >24 h; OR <24 h if available neuroimaging documents, a new haemorrhage or infarct; OR the neurological deficit results in death
- No other readily identifiable non-stroke cause for the clinical presentation (e.g. brain tumor, trauma, infection, hypoglycemia, peripheral lesion, pharmacological influences), to be determined by or in conjunction with the designated neurologist*
- Confirmation of the diagnosis by at least one of the following: neurologist or neurosurgical specialist; neuroimaging procedure (CT scan or brain MRI), but stroke may be diagnosed on clinical grounds alone

Stroke classification

- Ischemic: an acute episode of focal cerebral, spinal, or retinal dysfunction caused by infarction of the central nervous system tissue
- Hemorrhagic: an acute episode of focal or global cerebral or spinal dysfunction caused by intraparenchymal, intraventricular, or subarachnoid hemorrhage
- A stroke may be classified as undetermined if there is insufficient information to allow categorization as ischemic or hemorrhagic

Stroke definitions**

- Disabling stroke: an modified Rankin Scale (mRS) score of 2 or more at 90 days and an increase in at least one mRS category from an individual's pre-stroke baseline

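### Section 9.6 exempts serious TIAs from SAE processing as efficacy endpoints, but TIA is not an endpoint of this trial

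*Combined protocol and SAP*

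**What the plan says.** Section 9.6 sets the exemption. Its bracketed list of efficacy events reads "Serious events that are also efficacy endpoints (stroke, transient ischemic attack, SEE, and myocardial infarction", with bleeding added as a safety endpoint. These events "will be exempted from SAE processing and expedited reporting but will be captured in" the eCRF. The stated reason is that they are anticipated in this population and "will be periodically reviewed by the DSMB in an unblinded manner". The same section returns fatal SAEs to processing, whether or not they are exempt endpoints.

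The endpoints are in Section 7. The primary efficacy endpoint in 7.2 is "NACE, i.e., the composite of all-cause death, MI, ischemic stroke, SEE, valve thrombosis, and major bleeding (ISTH definition". The cerebrovascular endpoints in 7.4.1 are stroke and its subtypes, and the cerebrovascular part of MACCE is likewise "stroke (ischemic, hemorrhagic, or undetermined". Section 7.4.3 gives the scope of adjudication: "All relevant NACE components will be adjudicated by the CEC in a blinded manner".

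Section 17.3 defines TIA as an abrupt, focal, non-fatal deficit in the territory of one brain artery, "that lasts less than 24 hours and that does not satisfy the definition of stroke above".

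**The concern.** The exemption is granted to events on the ground that they are endpoints. For stroke, systemic embolic event (SEE) and myocardial infarction (MI) there is a sensible exchange: the event leaves the SAE stream and enters a planned, blinded, time-to-first-event comparison. If TIA is not an endpoint, it gives up the first and does not receive the second.

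The stake is modest but real. TIA is a thromboembolic signal, and this noninferiority trial compares two anticoagulants, so weaker protection on the new drug is one of the things a reader will look for. A site also cannot tell from Section 9.6 whether the words about efficacy endpoints govern, or the list in brackets. Sections 9.1 and 9.5.1 both send SAEs to 9.6, so the unclear text is the operative rule.

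**Working it through.** No arithmetic applies: the point depends on no rate, margin, alpha or sample size. The check is to set the exemption list beside the endpoint lists.

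| Event | Named in the 9.6 exemption | In the primary composite (7.2) | Secondary efficacy endpoint (7.4.1) |
|---|---|---|---|
| Stroke | Yes | Ischemic stroke | Yes, overall and by subtype |
| SEE | Yes | Yes | Yes |
| MI | Yes | Yes | Yes |
| TIA | Yes | No | No |
| Valve thrombosis | No | Yes | Yes |

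Of the four efficacy events named, three match Section 7 and one does not.

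**Is TIA an endpoint anywhere else?** It is not in the synopsis lists, the objectives in 2.1, the primary safety endpoint in 7.3, the secondary safety endpoints in 7.4.2, the other endpoints in 7.4.3, or 11.4.1. Outside 9.6, TIA appears as a definition (17.1.1.1 and 17.3) and in 9.12, as an example of a suspected adverse event.

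**Could a TIA be counted as a stroke?** Not under the TIA definition, which excludes events that meet the stroke definition preceding it. There is one boundary case. The general stroke definition in 17.3 needs symptoms beyond 24 hours or death, whereas the VARC-2 text in 17.3.1 also accepts a shorter deficit with an infarct or haemorrhage on imaging. A short event with an imaged infarct can therefore be read either way, and the two texts need reconciling.

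**What analysis do the matched events receive?** Under 11.4 and 11.4.2: time to first CEC-adjudicated event, Cox model, hazard ratio with 95% CI, in the ITT set over the overall study period. No such analysis is planned for TIA.

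**What remains for a serious TIA?**
- eCRF capture and periodic unblinded DSMB review (9.6).
- Site reporting within 24 hours of awareness (Table 17.1, footnote k).
- The general TEAE and SAE summaries (11.5.1). These use the Safety set, and an event more than 30 days after last dose is not a TEAE.
- Possible inclusion, though not as TIA, in the count of cardiovascular admissions of at least 24 hours (7.4.3).

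The rule that restores fatal events to SAE processing does not help here, because TIA is non-fatal by definition.

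**Which text governs?** If the words about efficacy endpoints govern, TIA follows normal SAE handling and valve thrombosis is exempt. If the bracketed list governs, the reverse holds. The protocol does not say which.

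**The case against.** The strongest reply is that Section 9.6 does not rest the exemption on adjudication or on a planned analysis. It says the events are clinically anticipated and under unblinded DSMB review, and that reasoning can cover TIA whether or not it is an endpoint. On this view only the label is wrong. This stands as a limit on the point, but it does not remove it. The rule still selects events by calling them efficacy endpoints, and for TIA that is untrue. Relabelling TIA as an anticipated event would cure the wording but leave it exempt without the analysis the other events receive.

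Four stronger readings are tempting, and the documents do not support them.

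- *A serious TIA goes unseen.* It does not: the safeguards listed above remain. Expedited reporting under 9.7 concerns suspected unexpected serious reactions, so the practical loss is chiefly SAE processing.
- *Every short neurological event is lost to the efficacy analysis.* Under the VARC-2 text, imaging-positive short events count as strokes.
- *Valve thrombosis should be added to the list for symmetry.* Nothing requires every endpoint to be exempt. Valve thrombosis is not on the list and, on that reading, gets full SAE processing. Adding it would remove that protection.
- *TIA must become an adjudicated secondary endpoint.* That is a preference. All secondary endpoints here are exploratory, and the contradiction can be cured without a new one.

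The CEC Charter, DSMB Charter and SAE Flow Plan are not among the documents. They may deal with TIA, so the practical consequence is less certain than the mismatch in the protocol text.

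**Conclusion.** The inconsistency is established: Section 9.6 exempts TIA as an efficacy endpoint, and Section 7 does not make it one. The consequence is limited. A non-fatal serious TIA loses SAE processing and expedited reporting without a compensating adjudicated analysis, while recording, prompt site reporting, DSMB review and descriptive summaries continue.

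The number of events cannot be given, because the protocol states no TIA rate. The primary composite, ISTH major bleeding, the margin of 1.38 and the four-step testing hierarchy are unaffected. The conclusion assumes that the bracketed list is applied as written and that the SAE Flow Plan and charters do not already handle TIA differently. It is worth correcting as a fault in a safety-reporting rule. It is not a threat to the trial's confirmatory conclusions.

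**What to change.** Delete transient ischemic attack from the bracketed list in Section 9.6, so that serious TIAs follow the normal SAE route, and align the SAE Flow Plan. In the same paragraph, state that valve thrombosis, although an efficacy endpoint, is outside the exemption and keeps full SAE processing; this settles whether the label or the list governs. The cost is a short amendment and a few more SAE reports. No endpoint, sample size or analysis changes.
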